Pre-Quit Counseling (~week 3). Participants will schedule their pre-quit session after completing the second MRI scanning session. During this visit participants will have their carbon monoxide (CO) assessed and will complete paper and pencil questionnaires (PANAS, MNWS, QSU & TLFB) in addition to attending a 1-hour semi-structured individual (in person) smoking cessation counseling session. Training and quality assurance measures will be established to ensure optimal delivery of the smoking cessation protocol. We will review audiotapes of sessions for the first 2 months of the trial and randomly throughout the trial to ensure protocol adherence and to prevent intervention drift. Counselor adherence to the treatment protocol will also be facilitated by use of highly structured protocols. The counseling session begins with a discussion of reasons for quitting, the model of smoking as a learned habit, triggers for smoking, and trigger management. Participants will receive brief training in how to manage withdrawal symptoms and relapse prevention counseling (e.g., identifying high risk situations or triggers to smoke, being prepared for and coping with high risk situations, limiting access to cigarettes, managing a slip and preventing a relapse, developing a personal relapse prevention plan, and managing a complete relapse). Smokers will also receive the NCI Clearing the Air self-help smoking cessation booklet. Counseling sessions may be recorded (audio) to ensure every participant is receiving the same standard of counseling. Participants will be informed if a counseling session is being recorded. The recording will be deleted after it is reviewed.

Monitoring Visits During 30-Day Abstinence Period (~Weeks 4-8). Beginning with the target quit date (TQD) (week 4) and weekly thereafter (weeks 5, 6, 7, 8), participants will attend a brief center visits. During the first week following TQD there will be two monitoring visits to closely monitor abstinence. These visits can be scheduled any time between 8am and 7pm. The entire session will last about 45 minutes.

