The target quit date session will be scheduled to occur up to 2 weeks following the pre-quit session. Prior to the booster counseling sessions, self-reported smoking will be assessed (time line follow back, CO, saliva cotinine and urinary cotinine); we will also administer self-report questionnaires (e.g., smoking urges, withdrawal and mood). Days to relapse (primary outcome) will be defined as number of consecutive days prior to 7-day relapse (7 consecutive days of smoking). Participants will then meet with a smoking cessation counselor for a 15 minute booster counseling session. Participants will receive small monetary incentives for each week of biochemically confirmed abstinence based on CO level (<=5ppm) and/or urine cotinine assessment (NicAlert, Nymox Pharmaceutical Corporation, Hasbrouck Heights, NJ) that also indicates no smoking during the past 7 days (\$75/week). Participants will be paid in cash after abstinence has been verified (and will not be paid for a missed visit). There is a \$50 bonus for participants who have attended at least 4 of the 5 in-person monitoring visits. Telephone assessments and counseling may be provided if participants miss a visit, at the discretion of the PI.

6 Month Follow-up (~Week 28). Participants who are biochemically verified to be quit at MV5 will be contacted 24 weeks post TQD by telephone to complete a brief survey of their smoking practices using the timeline follow-back assessment. Those who report not smoking a cigarette for at least the past 7 days prior to completing the survey will be asked to come to the Center for biochemical verification of smoking status by providing CO, saliva cotinine and a urine cotinine sample.

12 Month Follow-up (~Week 52). Participants who completed all visits up to and including the Pre-Quit visit will be contacted 48 weeks post TQD by telephone to complete a brief survey of their smoking practices and eating behavior. All measures collected at the 6 Month Follow-up will be collected with the addition two questions about readiness and intention to quit smoking (if applicable).

Table 2. Measures and Time Points

Activity	Phone Screen	Intake	fMRI Scans	Pre-Quit	TQD	MV 1-5	Follow-up	12-month Follow-up
Weeks	-1	0	1, 2	3	4	5, 6, 7, 8	28	52
Demographics		X						
Urine drug screen		X	X					
Urine pregnancy screen		X	X					
ETOH history/BrAC		X						
Height		X						
Weight		X						
Smoking behavior (FTND)		X						
Medical history form		X						

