Salivary testosterone: Salivary testosterone will be used to control for between-session differences that may occur due to change in testosterone levels in male and female participants. Testosterone (pg/ml) will be collected at the start of the scan session. Approximately 2 ml of saliva will be collected using a passive drool method and saliva collection aid (Salivette LLC, State College, PA, USA). The saliva will be stored in plastic vials at –20°C. Saliva samples will be assayed using testosterone EIA kits (Salimetrics LLC, State Collect, PA, USA). Salivary testosterone is highly correlated with plasma testosterone [55].

fMRI Measures: See fMRI Scanning Sessions above.

Primary Outcomes (Main Study): Multiple measures of abstinence will be measured for this study. The primary outcome will be the number of days to relapse following the target quit date. Relapse will be confirmed using a conventional SRNT guideline criterion of either a positive biochemical verification of smoking [3, 56] or 7 consecutive days of smoking based on self-report (it is very unlikely that a subject would meet the latter criterion without also meeting the former, given the long half-life of cotinine). The days to relapse will be based upon time from target quit date to the first day of the relapse period. Self-reported daily smoking data will be collected using a validated timeline follow-back method [57]. Self-reported abstinence will be biochemically verified on a weekly basis using urine cotinine (<100ng/ml) [56] and a CO reading

of ≤5PPM. Drop-outs will be considered relapsers following the last date of abstinence data provided [7, 58]. Secondary outcomes will include days to first “slip”, and cross-sectional measures of 7-day and 30-day point prevalence (biochemically verified weekly with cotinine, which provides an assessment of smoking in the last 7 days).

Carbon Monoxide (CO): The CO monitor is a handheld device that uses a disposable mouthpiece, reports CO in parts per million (ppm), and takes about 5 minutes to administer. Carbon monoxide measurements will be collected from smokers at each visit as a biochemical verification of smoking exposure.

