Urine Cotinine: Smoking status will be assessed with NicAlert™ urine dipsticks from Nymox Pharmaceutical Corporation. A midstream urine sample of approximately 25mL will be used to test for the presence of cotinine. Results will appear in one of seven category levels of usage. Level 0 indicates no detectable tobacco use; levels 1-2 indicate presence of cotinine, but as a non-user, and levels 3-6 indicate cotinine consistent with tobacco use. Participants with results in levels 3-6 will be considered smokers. Urine cotinine will be assessed at all Monitoring Visits 2-5, if participant has reported weekly abstinence.

Saliva Cotinine: Saliva cotinine will be collected to biochemically verify smoking status. Saliva samples will be collected at monitoring visits 2-5 from participants who report smoking abstinence and have a CO value of less than or equal to 5ppm.

Primary Outcomes (Recruitment & Retention Pilot Study):

Meeting Eligibility Criteria: The primary outcome is the percentage of subjects who meet final eligibility criteria (i.e., enrollment). We chose this as the outcome based on our data suggesting that subjects who meet these criteria are highly likely to reach ITT status.

Secondary Subjective Outcomes (Main Study):

Mood: Positive and Negative Affect: The Positive and Negative Affect Schedule (PANAS) [59], a 20-item Likert-format self-report measure, will be used to assess Positive Affect (PA; 10 items, e.g., enthusiastic, strong) and Negative Affect (NA; 10 items, e.g., distressed, upset), two dominant and generally orthogonal dimensions of affect.

Nicotine Withdrawal: The Revised Minnesota Nicotine Withdrawal Scale (MNWS-R) [60] is a fifteen-item self-report measure where participants rate their feelings of withdrawal on a scale of 0 (none) to 4 (severe). This measure will be administered at all study visits.

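### A cotinine test in the first week can reach back before the quit date, yet a positive test alone counts as relapse, so some true quitters could be given a false early event

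*Combined protocol and SAP*

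**What the plan says.** **Event.** Under Measures, Primary Outcomes (Main Study), relapse is confirmed by "either a positive biochemical verification of smoking" or, as an alternative, by seven self-reported smoking days in a row. No exception is made for samples taken soon after the target quit date (TQD). Time runs from the TQD to the opening day of the relapse.

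**Second definition.** The Monitoring Visits section defines the same primary outcome by seven smoking days in a row, with no biochemical trigger.

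**Look-back.** The Primary Outcomes paragraph describes point prevalence as "biochemically verified weekly with cotinine, which provides an assessment of smoking in the last 7 days". For the quit incentives, the Monitoring Visits section relies on a CO and/or urine cotinine result "that also indicates no smoking during the past 7 days".

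**Visit timing.** The Monitoring Visits section schedules center visits "Beginning with the target quit date (TQD) (week 4) and weekly thereafter (weeks 5, 6, 7, 8", and adds: "During the first week following TQD there will be two monitoring visits to closely monitor abstinence". Table 3 labels MV1 and MV2 both as week 5. No day is given for either.

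**First cotinine visit.** The Urine Cotinine paragraph says: "Urine cotinine will be assessed at all Monitoring Visits 2-5, if participant has reported weekly abstinence". The Saliva Cotinine paragraph names the same visits, limited to those who report abstinence and have CO of 5 ppm or less. Table 3 footnote 3 also starts NicAlert at MV2. The Monitoring Visits text, however, lists the assessments made ahead of booster counseling as "time line follow back, CO, saliva cotinine and urinary cotinine", without excepting MV1. Table 2 marks both cotinine assays in a single pooled column for MV1 to MV5.

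**The concern.** Participants are daily smokers at entry (at least 5 cigarettes a day, CO at least 8 ppm at Intake), and nothing requires them to stop before the TQD. A cotinine sample taken a few days after the TQD can therefore reflect smoking that was permitted. If a positive result is enough for relapse, a person who stopped on the TQD and stayed abstinent can be given an event in week 1.

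The error runs in one direction. Under the Measures section, cotinine is taken only from people who report abstinence (and, for saliva, have low CO), so carry-over can only turn an apparent quitter into a relapser. The affected outcome is time to relapse, the endpoint of the Aim 1 Cox models. The plan also gives no way to date a positive test with no reported smoking, because such a case has no opening day of relapse.

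**Working it through.** **1. The plan's own figure.** Power and Sample Size Considerations states 80% power with 200 participants, alpha 0.0085, effect size 0.25 or hazard ratio 1.32.
- Two-sided: n = ((2.63154 + 0.84162) / 0.25)² = 193.01, rounded up to 194. At n = 200, √200 × 0.25 − 2.6315 = 0.904, so power is 81.7% (80.9% by noncentral t). The figure reproduces.
- Hazard ratio 1.32 per SD: events = 3.47316² / (ln 1.32)² = 156.5, so 157, or 78% of 200. The plan states no event rate.

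This is context for step 5. Nothing here shows the power figure to be wrong.

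**2. Calendar.** With the TQD at week 4, day after TQD = 7 × (week − 4). The 6-month contact checks this: week 28 gives day 168, which is 24 weeks after the TQD, as stated. MV3, MV4 and MV5 (weeks 6, 7, 8) fall on days 14, 21 and 28. MV1 and MV2 (week 5) map to day 7 by label, but the text allows any day of the first week.

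**3. Pre-quit days inside a 7-day look-back** = max(0, 7 − test day).

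| Test day | 1 | 3 | 5 | 6 | 7 | 14 or later |
|---|---|---|---|---|---|---|
| Pre-quit days covered | 6 | 4 | 2 | 1 | 0 | 0 |

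If the participant smoked on the TQD itself, the first clear day is day 8.

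**4. Time to fall below 100 ng/ml**, the urine cut-off in Primary Outcomes. Days = (half-life in hours / 24) × log2(C0 / 100). The documents give neither half-life nor starting level C0, so both are assumptions.

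| C0 (ng/ml) | Days at half-life 16–24 h |
|---|---|
| 1000 | 2.2–3.3 |
| 2000 | 2.9–4.3 |
| 4000 | 3.5–5.3 |
| 8000 | 4.2–6.3 |

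Widening to 12–30 h and 500–8000 ng/ml gives 1.2–7.9 days. Within these assumptions, carry-over is common on days 1–3, possible on days 4–6, and uncommon by day 7.

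**5. Illustration of the effect on Aim 1.** Assumptions: 200 people, Weibull relapse times with shape 0.5, 180 days of follow-up, about 158 true events, hazard ratio 1.32 per SD, two-sided alpha 0.0085, false events placed at the test day and unrelated to the predictor, 6,000 replicates.

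| False positives among those still abstinent | Power, test on day 5 (about 152 abstinent) | Power, test on day 3 (about 162 abstinent) |
|---|---|---|
| 0% | 78.8% | 78.5% |
| 5% | 74.6% | 74.5% |
| 10% | 68.9% | 68.6% |
| 25% | 53.4% | 51.8% |
| 50% | 25.6% | 21.9% |

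At day 5, 10% is about 15 people (0.10 × 152). If cotinine clearance were related to the imaging predictors, the result could be bias as well as lost power; the documents do not settle that.

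**6. The two definitions side by side.** Take an early positive with no reported smoking. Under Primary Outcomes it is an event. Under Monitoring Visits it is not.

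**The case against.** The best defense is that the plan already keeps cotinine out of the first days.

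- *MV1 is skipped.* The urine and saliva paragraphs and Table 3 footnote 3 all start at MV2, with CO at every monitoring visit. Table 2's pooled column cannot show MV1 separately, and the Monitoring Visits list is general. This largely stands: the documents conflict in wording but do not establish that MV1 samples are taken.
- *MV2 may be meant for day 7.* Week 5 maps to day 7. The urine test depends on reported weekly abstinence, which can be read as needing a full week first. The first week's incentive is split $35 + $40 = $75, which suggests MV2 closes that week. This is a plausible intent, but no section fixes the day, and the saliva paragraph lacks the weekly condition.
- *Look-back is not positivity.* The seven-day phrase in Primary Outcomes describes secondary outcomes. A positive needs 100 ng/ml or NicAlert level 3 to 6; levels 1 and 2 count as non-user. This stands and limits the size.
- *The Monitoring Visits definition ignores biochemistry.* True, but this leaves two definitions of one primary event.

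A reader might go further and infer that every true quitter tested in week 1 is scored as relapsed at about day 0: with 40–60% of 200 abstinent, 80–120 false events. The documents do not support that. The 40–60% is an assumption, universal positivity is another, the assay paragraphs schedule no cotinine at MV1, and no rule dates such an event to day 0.

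**Conclusion.** The concern holds in a limited form. A stated rule for the primary outcome can count smoking before the TQD as relapse, because a positive test suffices, the first cotinine visit lies in the first week on an unfixed day, and early positives are not exempted. Some true quitters could be misclassified; the documents do not show that all or most would be.

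The size cannot be derived from the documents. Exposure is confined to week-1 samples before day 7 (day 8 for someone who smoked on the TQD). It is nil at MV3 to MV5 by the plan's own window, and nil at MV2 if that visit is held on day 7 and the person did not smoke on the TQD. The power losses in the illustration rest on its assumed relapse times and false-positive rates. The disagreement between the two relapse definitions needs no assumption and should be resolved in any case.

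**What to change.** 1. Reconcile the Monitoring Visits text, the Primary Outcomes, Urine Cotinine and Saliva Cotinine paragraphs, Table 2 and Table 3 footnote 3 to one first cotinine visit and one relapse definition. State the days of MV1 and MV2.
2. Then choose one of two routes. Either schedule the first cotinine test on day 7 or later after the TQD (day 8 if the participant smoked on that date). Or state in the outcome derivation that a positive from an earlier sample does not by itself count as relapse, and that status is then taken from CO (5 ppm or less) and timeline follow-back.
3. State how relapse is dated when a test is positive and no smoking is reported.
4. Add a sensitivity analysis that counts early positives as events.

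The derivation route costs wording and one programming rule; the scheduling route may also move MV2. Neither needs extra samples. The downside is that status before day 7 rests on CO and self-report, which detect less smoking than cotinine; the protocol itself uses CO at the abstinent scan to confirm only about 24 hours without smoking. Day 7 follows the protocol's own look-back. At the extreme of the assumed clearance range (7.9 days) a few carry-over positives could remain.

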participating research studies. All subjects will receive standard text messages and will be randomized to one of four groups (blocked within each study to ensure balanced groups): (1) Standard recruitment (SR): subjects will receive text messages ~2 days prior to their Intake visit with relevant information about the time, date, and location of the visit as well as contact information for study staff ("You have a study visit on [Date] at [Time]. Visit comp is \$10. Reply Y to confirm. See <http://j.mp/2222222> for reminders. Reply or appt may be canceled."); (2) SR + Information Provision (IP): Subjects will receive personalized messages designed to target injunctive norms regarding participating in research (e.g., "[Name], wondering why you should volunteer for research? Many find it a rewarding way to advance science and be a part of a community <http://j.mp/2222222>."); (3) SR + Contingency Management (CM): CM will be provided in the form of an opaque "lottery jar" with a high proportion of chips with little (\$1) monetary value. Participants draw from the lottery jar upon completion of an objectively verified target behavior (e.g., attending an Intake visit), and bonuses are often provided for continued performance [74, 75]. This strategy has been successful in augmenting visit compliance in several treatment studies [80-82]. All text reminders will be delivered using the Way 2 Health (W2H) software platform. Upon completion of all requirements for a given visit, participants will receive 5 lottery jar draws for that visit. Attendance at all visits earns participants bonus draws upon completion of the study. Failure to attend a visit without prior approval or failure to complete all visit requirements results in no draws for that visit. The lottery jar contains 500 chips: 250 say "good job," 219 have a value of \$1, 30 have a value of \$5, and 1 has a value of \$100. The study completion bonus will be 5 extra draws. Thus, at each visit, subjects will have the opportunity to make 5 draws from the lottery jar, for maximum possible earnings of \$120; (4) SR + IP + CM (IC): In this group, subjects will receive the targeted text messages and receive CM. The design of our study allows us to examine each strategy independently as well as combined to evaluate the optimal approach.

3. Study Duration

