Shipley Institute of Living Scale		X						
Psychiatric hx		X						
Adverse Childhood Experiences Questionnaire		X						
Intention to quit smoking		X						
Impulsivity		X						
Anxiety			X					
Magnet safety form		X	X					
Emergency contact form		X						
Saliva NMR		X						
Salivary cortisol (nmol/l)			X					

Salivary estradiol pg/mL			X					
Salivary testosterone pg/ml			X					
fMRI								
Resting BOLD			X					
Working Memory (Fractal N-back)			X					
Cue Reactivity			X					
Stress Reactivity			X					
Primary Outcomes								
Carbon monoxide (CO)		X	X	X	X	X	X	
Urine Cotinine						X	X	
Saliva Cotinine						X	X	
Smoking rate (TLFB)		X	X	X	X	X	X	X
% Eligible at Intake (pilot)		X						
Secondary Outcomes								
Mood (PANAS)		X	X	X	X	X	X	X
Withdrawal (MNWS)		X	X	X	X	X	X	X
Smoking urges (QSU-B)		X	X	X	X	X	X	X
Attitudes toward research (pilot)	X				X		X	
Compared riskiness scale (pilot)	X	X						
Perceived coercion scale (pilot)		X						
Previous experience research studies (pilot)	X							
Prior persuasion questions (pilot)		X						
Personal financial wellbeing (pilot)	X							
Previous experience research studies (pilot)	X							
Intention and Readiness to Quit Smoking								X

Measures

Screening/Covariates:

Demographics: Standard surveys will collect demographics (e.g., age, education, race, and gender).

Urine Drug Screen: A urine sample will be collected at all study visits to conduct a urine drug screen. The urine drug screen indicates whether the subject has recently taken any of the following drugs or medications: THC, cocaine, opiates, PCP, benzodiazepines, methadone, MDMA, amphetamine, methamphetamine, tri-cyclic antidepressants, OxyContin and/or barbiturates. Participants with a positive urine drug screen for any exclusionary substance will be deemed ineligible (See Key Exclusionary Criteria; Alcohol/Drugs). In an effort to remain CLIA-compliant, results from urine drug screening will not be shared with participants. Participants will be informed that the testing is for research purposes only and that they will be informed of their eligibility status, but not of the specific testing results.

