Smoking Urges/Craving: The 10-item brief QSU-B questionnaire on smoking urges [61] will be administered at the same time points to assess cravings to smoke. The QSU-B contains 2 subscales (anticipation of reward, relief from negative affect). During the fMRI scans (prior to and following the cue reactivity task), participants will also be asked to rate the severity of their urges to smoke using two 4-point Likert scale items: “cravings for a cigarette” and “urges to smoke at this time” (0=not present, 3=severe). These 2 items have been related to smoking cessation outcomes [62] and resting cerebral blood flow in our prior study [63], and are feasible to assess as a brief measure in the MRI scanner.

Stress/Anxiety: Anxiety will be measured at both fMRI scanning sessions using the State-Trait Anxiety Index [64], which has been used as a covariate in fMRI studies of stress response [52].

Participants will be asked to rate “how stressed do you feel right now” on a scale from 0-100 immediately before and after the MIST.

Readiness/Intention to Quit Smoking: two questions will be asked at the 12-month follow-up survey to assess readiness to quit smoking and intention to quit smoking. The readiness questions is asks on a Likert scale from 1 – 9 the participant’s current thinking about smoking (1 = taking action to quit, 9 = no thought of quitting). The intention to quit smoking questions asks how likely the participant is to try to quit in the next 30 days on a Likert scale from 1 -- 4 (1 = very unlikely, 4 = very likely). The two questions will be asked regardless of study-quit status.

Secondary Subjective Outcomes (Recruitment & Retention Pilot Study):

Impressions of Research: Attitudes towards research; motivations for participation; perceived risks/benefits of research; personal financial wellbeing and perceptions of influence or coercion will be assessed via text survey at baseline (following phone screen), mid-way through participation and at study completion. Study staff will attempt to contact subjects who withdraw or are lost-to-follow up to identify reasons for withdrawal. We will assess overall satisfaction with the study, acceptability of the frequency and content of messages (IP and IC groups only). For all models, a term will be included for individual study as well as other relevant covariates (e.g., sex, age, income).

2. Statistical Analysis

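### The pilot's attitude, risk, financial and coercion measures follow two conflicting schedules, and on the natural reading of Table 2 perceived coercion and later attitudes are measured only after events the arms are meant to change

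*Combined protocol and SAP*

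**What the plan says.** The paragraph on impressions of research, under Secondary Subjective Outcomes (Recruitment & Retention Pilot Study), lists attitudes to research, motivations, perceived risks and benefits, financial wellbeing and perceived influence or coercion. All of them "will be assessed via text survey at baseline (following phone screen), mid-way through participation and at study completion". The list plainly includes the last two: "personal financial wellbeing and perceptions of influence or coercion will be assessed via text survey".

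Table 2 places the corresponding rows under Secondary Outcomes and schedules them measure by measure: attitudes at phone screen, target quit date (TQD, week 4) and Follow-up (week 28); compared riskiness at phone screen and Intake; perceived coercion at Intake; personal financial wellbeing at phone screen.

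On who is contacted at week 28, the 6 Month Follow-up paragraph says: "Participants who are biochemically verified to be quit at MV5 will be contacted 24 weeks post TQD by telephone". On what the contingency management (CM) arms reward, the Design section says: "Participants draw from the lottery jar upon completion of an objectively verified target behavior (e.g., attending an Intake visit". The pilot's hypothesis is higher enrolment in the intervention arms, and its primary outcome is the percentage meeting final eligibility criteria.

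**The concern.** There are two problems.

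First, staff cannot follow both schedules. For coercion, riskiness and financial wellbeing, the text and Table 2 differ in the number of assessments and in their timing.

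Second, if Table 2 is followed, the later assessments come after events that the randomised arms are designed to influence. People whom an incentive or a message brought to Intake are in the data for their arm, while their counterparts in the standard recruitment (SR) arm are not. A difference between arms in perceived coercion or attitudes could then reflect who came and not how the strategy made people feel. Perceived coercion is the measure most directly relevant to a cash lottery, and Table 2 collects it once, after the first rewarded behaviour.

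**Working it through.** **Step 1. The two schedules side by side.**

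| Measure | Outcomes text | Table 2 | Agreement |
|---|---|---|---|
| Attitudes | baseline, mid-way, completion | phone screen, TQD, week 28 | can be matched |
| Perceived risk | baseline, mid-way, completion | phone screen, Intake | conflict |
| Coercion or influence | baseline, mid-way, completion | Intake only | conflict |
| Financial wellbeing | baseline, mid-way, completion | phone screen only | conflict |

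The text puts baseline after the phone screen, so Table 2's single coercion assessment at Intake is not the text's baseline either.

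**Step 2. What completion means.** Three end points are possible. Table 3 places the completion bonus draws at Monitoring Visit 5 (MV5, week 8). Table 2 places the last attitudes assessment at week 28. Study Duration extends participation to about 12 months for those who complete the Pre-Quit Visit. The 12-month contact reaches everyone who completed visits through Pre-Quit, but Table 2 marks no attitudes assessment there.

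**Step 3. Who can supply each Table 2 assessment, on its natural reading.**

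- Phone screen (attitudes, riskiness, financial wellbeing): everyone randomised.
- Intake (coercion, second riskiness): those who attend Intake.
- TQD (second attitudes): those who are found eligible and stay in the study to the quit date.
- Week 28 (third attitudes): those contacted then, limited to participants verified quit at MV5.

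**Step 4. How many could reach TQD.** The pilot power paragraph gives 576 participants, 28% enrolment in SR and a detectable difference of 12 percentage points. I assume equal arms, that those randomised are those who schedule an Intake, and that all four participating studies use this study's schedule.

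- Per arm: 576 / 4 = 144.
- SR enrolled: 144 × 0.28 = 40.3.
- Information provision (IP) or CM enrolled: 144 × (0.28 + 0.12) = 144 × 0.40 = 57.6.

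So at most about 40 and 58 of 144 could give the TQD attitudes assessment. The documents give no Intake attendance rate and no expected quit rate at MV5, so no such count can be given for the Intake coercion scale or for week 28.

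**Step 5. What the size of the bias depends on.** Suppose everyone who would enrol under SR would also enrol under IP or CM (an assumption). The share of IP or CM enrollees whom SR would not have enrolled is then 1 − 0.28 / 0.40 = 0.30. If these extra enrollees differ from the others by d standard deviations (SD) on an attitude score, the arm contrast at TQD shifts by 0.30 × d with no true effect. For assumed d of 0.25, 0.5 and 1.0, this is 0.075, 0.15 and 0.30 SD. The sampling standard error of that contrast is about √(1/40.3 + 1/57.6) = 0.21 SD. The documents say nothing about d, so this shows how the bias would arise and does not estimate it. It does not apply to coercion, where the selection is on Intake attendance.

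**Step 6. Whether an analysis deals with this.** The outcomes paragraph adds terms for study and for covariates such as sex, age and income. The missing-data section imputes survey items missing at random and expects few dropouts. Subjects who withdraw or are lost are contacted for their reasons. None of this covers an assessment missed because the person never reached the visit.

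**The case against.** The strongest reply is that the documents never make the surveys depend on attendance. They go by text, and the verified-quitter rule governs a telephone call about smoking. A text could be sent to everyone at week 28. This stands as far as it goes: restriction to attenders is the natural reading of a visit-based table, since someone who never enrols has no quit date, but it is not stated. The protocol needs to say who receives the texts.

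A second reply is that the pilot states one aim, enrolment rates, and specifies no arm contrast or time trend for these measures. This also stands. The criticism is conditional: any comparison by arm would suffer. Models with a study term are nevertheless foreseen, and both the text and Table 2 label the measures secondary outcomes.

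A third reply is that perceived coercion about joining belongs at Intake, where consent is given, and that financial wellbeing is reasonably a baseline measure. Both are fair, and the fix keeps the Intake scale.

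A reader might infer more than the documents support:

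- That one measure narrows from all randomised to Intake attenders, then quit-date attenders, then verified quitters. None does. Attitudes have no Intake mark, and coercion is measured once, so it has no trend.
- That only a handful of people per arm would remain at week 28. This needs a quit rate at MV5. The abstract's figure of under 25% is for nicotine replacement therapy; this study excludes its users and pays for verified abstinence, so it is not a ceiling here.
- That the same loss applies to the whole pilot. Table 2 and the week-28 rule describe one of four participating studies.

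**Conclusion.** The schedule conflict for coercion, riskiness and financial wellbeing is established from the text alone and needs no assumption. For attitudes the two sources can be reconciled, apart from the undefined end point.

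The selection concern holds on the natural reading of Table 2: the coercion scale and the later attitudes assessments come after Intake attendance or enrolment, which the arms are meant to change. A comparison by arm would then not compare the randomised groups. Its scale is bounded only at TQD (at most about 40 against 58 of 144 per arm, under the Step 4 assumptions). The bias itself cannot be sized from the documents. The pilot's primary outcome is unaffected, so this is a matter of secondary outcomes that is worth correcting.

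**What to change.** 1. Reconcile the outcomes paragraph with Table 2, measure by measure, and define mid-way and completion as dates. If financial wellbeing is meant as a baseline measure only, the text should say so.
2. Send the later attitude items and the perceived-influence and risk items by text to all randomised participants at fixed times from randomisation, whether or not they attended, enrolled or quit.
3. Keep the consent-specific coercion scale at Intake and label it as descriptive among attenders.
4. Analyse the texted items by randomised arm and report response rates by arm.
5. State whether the other three participating studies follow the same schedule.

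The cost is a corrected table, a short analysis statement and some automated messages on the Way to Health platform already in use. Pilot eligibility already requires a phone that receives texts and consent to receive them. The downside is some non-response among people who did not attend, which the response rates by arm would make visible.
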